6.7 Concomitant interventions

Both intervention and control companies will be free to engage with and become involved with any other interventions they wish. If the research team becomes aware that a participating company is involved with another relevant nutrition intervention or programme, the name of the programme, the date(s), type, and level of involvement will be recorded in the study database.

6.8 Withdrawal criteria

Companies will be free to withdraw from receiving the intervention or engaging with the research team at any point. If, through the course of the study, there are compelling reasons (e.g., emerging and substantial conflicts of interest) for the research team to withdraw companies from participating in the trial, this will be discussed by the Steering Group Committee, and, if agreed, recorded in a study database and noted in all publications.

6.9 Baseline assessments

Baseline assessments will be conducted for all randomised companies utilising publicly available, routinely collected data where possible, including:

- Relevant company demographics and information (company name, key brands, product categories, category market share, category sales revenue, head office location)
- Baseline product portfolio information (number of products, average nutrient content per 100g (energy, saturated fat, sodium, total sugar, fibre etc.), mean estimated HSR, % products displaying HSR)
- Company nutrition-related policies and commitments

6.10 Primary outcome measure

The primary outcome measure will be the nutrient profile (measured using the Australasian Health Star Rating (HSR) system) of the foods and beverages produced and sold by participating food companies at 24 months post-baseline.

In 2014, New Zealand and Australia adopted the HSR, a voluntary, interpretive front-of-pack nutrition labelling system. HSR rates the nutrition content of packaged food and beverages in half-star increments from half a star (least healthy) to five stars (most healthy). The number of stars displayed is calculated based on the energy, saturated fat, total sugar, sodium, and fruit, vegetable, nut, and legume (FVNL) levels in a product and, in some instances, the protein and fibre content (32). The most recent version of the HSR calculator will be used. The nutrient data to estimate HSR will be extracted from the New Zealand Nutritrack and Australian FoodSwitch databases, which contain annually updated Nutrition Information Panel values, ingredients, and labelling information for packaged products available for sale in major supermarket stores each country.

6.11 Secondary outcome measures

The following secondary outcome measures will also be collected and assessed:

- Nutrient profile (measured using the HSR system) of the foods and beverages produced and sold by participating food companies at 12-months post-baseline.
- Nutrient content (including sodium, sugar, and saturated fat) of the foods and beverages produced by the food companies at 12- and 24 months post-baseline. The nutrient data will be extracted from the New Zealand Nutritrack and Australian FoodSwitch databases.
- Display of HSR labels on packaged foods and beverages produced by the food companies at 24 months post-baseline.
- Company nutrition-related policies and commitments at 24-months post-baseline, measured using the validated BIA (Business Impact Assessment)-Obesity tool (22). Publicly available data related to company policies and commitments to improve population nutrition will be assessed at baseline. Surveys (control and intervention companies) will be used to collect data at 24 months post-baseline. Policy areas include product formulation, product labelling, marketing to children and accessibility (price and availability) of healthy and unhealthy food.
- Company engagement with the intervention and reported, mechanisms, enablers, and barriers to improving nutrition-related policies and practices will be measured via the process evaluation interviews and surveys. Data collection for intervention food companies will occur via survey at baseline and 24 months post-baseline. Control companies will receive a survey at 24 months post-baseline only. Representatives from selected intervention and control companies will be invited to participate in in-depth interviews at

24 months post-baseline. Key indicators will be change relative to baseline in company prioritization and motivation for change, and change mechanisms and resources.

- Information on resources used to develop the awards/recognition programme, implement the intervention, and those accrued by intervention companies will be collected using resource use questionnaires. Resource use data and the primary outcome estimate will be used to conduct a within-trial cost-effectiveness analysis and a modelled analysis incorporating the population health impact of the intervention.

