A core component of the intervention will be a tailored support programme. This will include company-specific reports on the nutrient profile of a company's product portfolio, their adoption of HSR, and their rankings compared to those of competitor companies (using data sourced from the Nutrtrack and FoodSwitch databases). Intervention companies will also be provided with detailed and specific advice on ways to improve their other nutrition-related policies and practices that will draw upon a detailed assessment of company policies and areas for improvement, and the provision of exemplars of both international and national good practice in each domain (e.g., case studies of successful product reformulation efforts). Intervention companies will receive relevant customer insight data and where appropriate, will be provided with information on existing networks, workshops, and support mechanisms of relevance to their industry sector in each country. All intervention materials will be developed in partnership with stakeholders with expertise in consumer campaigns and advocacy. The intervention will span 12 months, but study outcomes will be measured at 24 months to maximize the time available for companies to enact changes.

One of the opportunities presented to intervention companies as a reason to engage with the research team, will be input into the development of a nutrition-related awards/recognition programme. The details of the awards/recognition programme will be developed iteratively as part of the study. It is expected to consist of a list of pre-defined pledges that companies will be

encouraged to sign up to, with annual auditing and renewal of pledges and practices. It is envisaged that the awards/recognition programme will be sector-specific, based on best practice evidence from a public health perspective, and will have independent governance arrangements.

- **Control group**

The control group will not be contacted or offered the intervention during the trial. Generic intervention resources produced for the study, including guides, case studies and referral networks, will be made available to control companies at 24-months post baseline. In addition, an overview of intervention outcomes including ‘lessons learned’ will be offered to all intervention and control companies.

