6.6 Blinding

Neither intervention nor control companies will be aware of the RCT design. Due to the nature of the intervention, food companies allocated to the intervention group will be aware of the programme, as will research staff who engage with the companies. Food companies allocated to the control group will not be contacted during the trial intervention period. Outcome assessments on the foods and beverages produced and sold by all trial food companies will be conducted independently using the Australasian Health Star Rating (HSR) nutrient profiling system, and information extracted from country-specific food product databases (New Zealand Nutritrack databases and Australian FoodSwitch database).

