The FoodSwitch dataset contains nutrient information obtained directly from the NIP of all packaged food and beverage products available for sale from five large supermarket retailers in Sydney, Australia (Woolworths, Coles, Aldi, IGA and Harris Farm). Data are collected by trained personnel during the months of August to November each year. For each product, the product name, package size (g), and nutrient content per 100g/mL and per serve are recorded. Food and beverages are classified according to a hierarchal system to classify products into major categories (e.g., dairy), minor categories (e.g., milk), major subcategories (e.g., soy milk) and minor subcategories (flavoured soy milk) (36, 37).

7.3.3 *BIA-Obesity*

Assessment data relating to food company policies will be collected from publicly available information obtained from company websites and other online sources, or directly from company representatives (at follow-up only). Although individual participant information may be collected to facilitate communication and to arrange any phone calls or meetings as necessary, no additional identifying information will be collected throughout the process. Names of company representatives will not be released. In some cases, companies may request that commercial in confidence information that they provide to the research team be used only for the purposes of the study and scoring using the BIA-Obesity tool, but not for other purposes.

7.3.4 *Process evaluation*

For ease of consultation with colleagues and completion, surveys will be paper-based (fillable PDF) and emailed to company representatives to fill out via computer or legibly by hand. Each company will be assigned a unique study ID which will appear on the survey. Once completed, company representatives will be asked to (scan if completed by hand) and email the completed survey to the research team. Scanned email responses and survey will be saved on a secured restricted folder at The University of Auckland or Deakin University.

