Companies will be asked to nominate a contact person for the research team. This contact person will be introduced to the study, via email or phone conversation. At this point, they will be asked to sign a Plain Language Statement/Individual Consent Form and Organisational Consent/Permission Form, and return it to the research team. It will be made clear that even though a company may choose to participate in the research, the company representative can choose not to. They will also be informed of their right to withdraw from “participating” in the study at any time by communicating that to the research team, but will be informed that the company will still be included in the study based on publicly available data related to the company, and interview data with the company if they withdraw over one month after interviews are conducted. Company representatives will also be provided with the contact information of the principal investigators and the Office of Research Ethics. Although individual participant information may be collected to facilitate communication and to arrange any phone calls or meetings as necessary, no additional identifying information will be collected throughout the process. Names of those involved in the study will not be released.

Control companies will not be contacted by the study team during the intervention phase. At 24 months post baseline, control companies will be invited to provide information on nutrition-related policies and practices, following a similar informed consent process, and following a similar data collection process, as outlined above for intervention companies at 24 months.

8. Assessment of Safety / Adverse Event Reporting

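### The 24-month BIA-Obesity score may include information that companies volunteer, so unequal disclosure between arms could bias this secondary comparison

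*Protocol*

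**What the plan says.** Company policies and commitments at 24 months, scored with the BIA-Obesity tool, are a secondary outcome (Protocol Section 6.11). For baseline, that section says "Publicly available data related to company policies and commitments to improve population nutrition will be assessed at baseline". For follow-up it says "Surveys (control and intervention companies) will be used to collect data at 24 months post-baseline". Section 7.3.3 describes the sources differently: company websites and other online material, "or directly from company representatives (at follow-up only". It also foresees companies handing over commercially confidential material for use in the scoring.

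The arms reach the 24-month survey by different routes.

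- **Control companies.** Section 7.4.3 says "Control companies will not be contacted by the study team during the intervention phase", and then "At 24 months post baseline, control companies will be invited to provide information on nutrition-related policies and practices". The invitation is voluntary and needs consent.
- **Intervention companies.** They are approached at the start, and those that take part nominate a contact person and sign consent forms (Section 7.4.3). Section 6.4 says "Intervention companies will also be provided with detailed and specific advice on ways to improve their other nutrition-related policies and practices". The Section 2 schematic and Appendix 3 list BIA-Obesity assessments and criteria among the resources these companies receive.

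On blinding, Section 6.6 says "food companies allocated to the intervention group will be aware of the programme, as will research staff who engage with the companies". Independent outcome assessment is stated there for the food and beverage outcomes only. Section 7.2.2 compares secondary efficacy outcomes between arms with adjustment for the baseline value.

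**The concern.** A policy score can rise because a company improved its policies, or because the scorer was told about policies that were not public. The second route opens only at follow-up and depends on what each company chooses to supply. A company that has worked with the team, and has been shown the tool's criteria, is plausibly readier to answer and better informed about what earns points than one hearing from the team for the first time. If so, part of the between-arm difference reflects disclosure rather than policy.

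At stake is the interpretation of one secondary outcome, although it is the only between-arm measure of the policy domains outside composition and labelling that the intervention targets. The primary outcome is computed from the Nutritrack and FoodSwitch databases and does not depend on company cooperation.

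**Working it through.** **Figures in the plan.** The protocol gives power for the primary outcome only, and none for the BIA-Obesity score. The primary figures reproduce. The design effect is 1 + (10 − 1) × 0.4 = 4.6 and the SD of a company mean is 1.25 × √(4.6/10) = 0.848. For a difference of 0.48, a normal approximation gives 90.5% power with 100 v 50 companies and 80.8% with 50 v 50, against the stated 90% and 80%. This point does not depend on them.

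**Sources side by side.**

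- Baseline, both arms: public information only (Sections 6.11 and 7.3.3).
- 24 months: Section 6.11 names surveys in both arms; Section 7.3.3 allows public information or company-supplied information. The two do not quite agree, and neither states a public-only score for every company.
- Contact before 24 months: none for control companies during the intervention phase; continuing for engaged intervention companies.

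**Form of the bias.** Suppose there is no true policy effect and companies that do not respond are scored on public information. Let g be the score gain from volunteered information, and rI and rC the response proportions in the intervention and control arms. Then

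bias = g × (rI − rC).

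The baseline score appears nowhere in this expression. Adjusting for it therefore leaves the term in place, and would do so however the baseline had been scored. If rI = rC and g is the same in both arms, the bias is zero.

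**Illustration with assumed values.** The documents give neither g nor any survey response. I take g as 0.25, 0.5 or 1.0 company-level SD, intervention response as 50% and control response as 30% or 10%. The 50% borrows the protocol's estimate of programme uptake (Section 7.1), which is not a survey response rate. The standard error in SD units for 100 v 50 companies is √(1/100 + 1/50) = 0.173, and the test is two-sided at 5%.

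| Response (I v C) | g (SD) | Bias (SD) | False-positive rate |
|---|---|---|---|
| 50% v 50% | any | 0 | 5% |
| 50% v 30% | 0.25 | 0.25 × 0.20 = 0.05 | 6% |
| 50% v 30% | 0.5 | 0.5 × 0.20 = 0.10 | 9% |
| 50% v 30% | 1.0 | 1.0 × 0.20 = 0.20 | 21% |
| 50% v 10% | 0.25 | 0.25 × 0.40 = 0.10 | 9% |
| 50% v 10% | 0.5 | 0.5 × 0.40 = 0.20 | 21% |
| 50% v 10% | 1.0 | 1.0 × 0.40 = 0.40 | 64% |

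Only the gap in response matters: 70% v 30% gives the same results as 50% v 10%. If non-responders were dropped instead, the comparison would be confined to companies that chose to respond, a selection problem that this formula does not describe.

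**The case against.** The strongest reply is that both arms are measured in the same way at follow-up. The survey goes to both, and Section 7.4.3 gives control companies a similar collection process. A reader might infer that the change of source between baseline and 24 months is itself the bias. The documents do not support that: a public-only baseline is a legitimate covariate in a randomised comparison, and with equal disclosure the bias is zero. The only route is differential response or completeness, on which the protocol gives no figures. This part of the reply stands and limits the point to a risk.

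Two further replies stand in part. Section 7.3.3 does not exclude public information at follow-up, so the 24-month score need not be survey-only; the two sections need aligning. Section 4 describes BIA-Obesity as involving extensive engagement with companies, so public-only scoring omits part of the tool's usual process. The baseline already omits it, however, so public-only is the version available on the same footing at both times.

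A reader might also object that the mixed model's company random effect cannot be estimated with one policy score per company. The protocol does not say that there is only one score (the tool has several domains), and the model form for each outcome is ordinary content for the statistical analysis plan. No finding is made on that.

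**Conclusion.** The concern holds as a foreseeable risk to one secondary comparison. Voluntary disclosure feeds the 24-month score, the arms come to that request with very different histories, and no like-for-like score is stated. The direction is plausibly in favour of the intervention, but the size cannot be derived from the documents. Across the assumed values it runs from 0 to 0.40 SD. Because only about half of the intervention arm is expected to engage, the intention-to-treat comparison is partly protected; the per-protocol comparison, confined to intervention companies that engaged, is more exposed.

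A reader might conclude that a positive policy result could never be attributed to policy change. That goes too far: a difference clearly larger than the plausible disclosure gain multiplied by the observed response gap would not be explained away. The primary Health Star Rating outcome is not touched.

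**What to change.** Align Sections 6.11 and 7.3.3 so that all 150 companies are scored at 24 months from public information by the baseline procedure. Use that score, adjusted for the public-only baseline score, for the between-arm inference. Report the survey-augmented score alongside it as supplementary, with response by arm. Where existing staff allow, have the public scores coded without knowledge of allocation.

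The cost is a change of wording and one repeat of the baseline scoring. It needs no company consent and takes survey non-response out of the main comparison. There are two downsides. Unpublished policies would not count in the compared score. Intervention companies, having been advised on policy, may also publish more without changing practice, so the disclosure bias is reduced but not fully removed.

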6.12 Schedule of intervention and follow-up

Companies will be approached in the first half of 2021 and the intervention will start from Q2 or Q3 2021, and will run for 12 months.

Trial assessments will be undertaken at baseline, and at 12 months and 24 months post-baseline [Table 1].

In New Zealand, the 2019 Nutritrack dataset will be used for baseline assessment of the primary outcome, and the 2022 and 2023 datasets (collected Q1/2 each year) will be used for the 12-month and 24-month primary outcome assessments. In Australia, the 2019 FoodSwitch dataset will also be used for baseline assessment of the primary outcome, and the 2021 and 2022 datasets (collected Q4 each year) will be used for the 12-month and 24-month primary outcome assessments. Data collection was disrupted in both countries in 2020 due to COVID-19, and thus the 2019 datasets were selected for use as a baseline.

Table 1: Details of follow-up

Timing		0 weeks (2021)	12 months (2022)	24 months (2023)
Description	Screening + Engagement (intervention companies only)	Baseline data collection + Randomisation (all companies)	Interim follow-up (all companies)	Final follow-up (all companies)
Approach to intervention company				
Obtain intervention company representative contact details	✓			
Send introductory email and follow-up to seek engagement	✓			
Confirm engagement with programme	✓			
Company description				
Company demographics		✓		
Product portfolio information		✓		
Outcome assessments				
Nutrient profile of company product portfolio (mean Health Star Rating)		✓ (2019 datasets)	✓ (2022 dataset NZ, 2021 dataset Aus)	✓ (2023 dataset NZ, 2022 dataset Aus)
Nutrient content (including sodium, sugar, and saturated fat) of the foods and beverages		✓	✓	✓
% products displaying HSR		✓		✓
Nutrition-related policy and commitment scores (BIA-Obesity assessment)		✓		✓
Level of company prioritization and motivation for change; enablers and barriers		✓ (intervention companies only)		✓
Resources associated with intervention and relevant actions undertaken by control companies			✓ (resource use data for intervention company actions collected over the 12 months of the intervention)	✓

7. Statistical Considerations

7.1 Sample size

A total of 150 food companies across both countries (intervention n=100, control n=50) will provide 90% power at a 5% level of significance to detect a minimum 0.48-unit difference between two randomised groups in the mean HSR of all packaged food and beverage products at the end of intervention, assuming a mean HSR of products of 2.95, a standard deviation (SD) of 1.25, and an intra-cluster correlation (ICC) between products produced by the same company of 0.4. This effect size would constitute an approximate 16% increase in the star rating (healthiness) of foods produced by the intervention companies compared to the foods produced by the control group companies.

We estimate that about half of the intervention companies will participate in the intervention programme, which will reduce the effective sample size. A total of 100 companies (50 intervention and 50 control companies) will provide 80% power to detect the expected effect size on the primary outcome under the same assumptions.

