A total of 150 companies (intervention n=100, control n=50) across both countries, with a minimum of 10 products per company, will provide 90% power at a 5% level of significance to detect a minimum 0.48-unit difference between groups in the mean HSR of all packaged food products over the 24-month follow-up period, assuming a mean HSR of products of 2.95, a standard deviation (SD) of 1.25, and an intra-cluster correlation (ICC) between products produced by the same company of 0.4. This would constitute an approximate 16% increase in the star rating (healthiness) of foods produced by the intervention companies compared to foods produced by the control group companies.

We estimate that about half of the intervention companies will participate in the intervention programme, which will reduce the effective sample size. A total of 100 companies (50 intervention and 50 control companies) will provide 80% power to detect the expected effect size on the primary outcome under the same assumptions.

Statistical analysis

Trial analyses will be conducted on an intention-to-treat (ITT) basis, following the CONSORT 2010 statement guidance with extension to cluster randomised trials. All randomised companies will be included in the primary ITT analysis. A per-protocol (PP)

analysis will also be conducted including only those intervention companies that participate in the intervention programme as per protocol.

Descriptive information will be presented at both company and food category level by treatment group pre- and post-intervention. Primary and secondary efficacy outcomes will be tested between intervention and control groups using generalised linear mixed models. The fixed effects will include treatment group, stratification factors, baseline outcome value and key food categories. Food company will be included as a random cluster effect. The ICC coefficients will be estimated using the trial data. The size of any intervention effect will be estimated overall and by key food categories. Country-level analysis will also be undertaken.

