7.2 Statistical analyses

Trial data collected from both countries will be stored in secure study databases before being merged and analysed by the study statistician at NIHI. Statistical analysis will be performed using SAS version 9.4 (SAS Institute Inc., Cary, NC, USA).

Data analyses will be carried out on an intention-to-treat (ITT) basis. All 150 randomised companies will be included in the primary ITT analysis. A per-protocol (PP) analysis will also be conducted including only those intervention companies who participate in the intervention programme, defined in this instance as agreement to participate in the programme and attendance at minimum one meeting regarding the intervention. A statistical analysis plan prepared by the study statistician (and agreed upon by the Steering Committee) will be prepared a priori. The CONSORT 2010 statement (33) with extension to cluster randomised trials guidelines will be followed when reporting the main trial results.

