7.2.1 Baseline characteristics

Baseline data collated for all randomised companies will include:

- Company demographics and information (company name, key brands, product categories, category market share, category sales revenue, head office location)
- Baseline product portfolio information (number of products, average nutrient content per 100g (energy, saturated fat, sodium, total sugar, fibre etc.), mean estimated HSR, % products displaying HSR or other nutrition label)

Data collected at both company and food category level will be summarised descriptively by treatment group. Continuous variables will be presented as numbers of observations, means, standard deviations (SD), medians and ranges. Categorical variables will be presented as frequencies and percentages. Simple tests comparing two groups at baseline will not be undertaken as per the CONSORT guidelines. Such tests also do not consider the clustered nature of the data in a cluster randomised trial.

7.2.2 *Intervention effects*

All food companies will be included in the group they were allocated to, in order to determine the effects of the provision of tailored support to food companies on their nutrition-related policies and practices, compared to no intervention. Both primary and secondary efficacy outcomes will be tested between intervention and control groups using generalised linear mixed models. The fixed effects will include treatment group, stratification factors, baseline outcome values, and key food categories. Food company will be included as a random cluster effect. The size of any intervention effect will be estimated overall and by key food categories. Model-adjusted group differences will be reported with 95% confidence intervals and p-values, and the ICC coefficients will be estimated. Statistical tests will be two-sided at a 5% significance level.

Pre-specified subgroup analysis will be conducted for each country separately. A secondary analysis will examine only products available over the full duration of the intervention period.

7.2.3 *Economic analyses*

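### The 80% power in section 7.1 belongs to the 50 v 50 per-protocol comparison, not to the primary ITT analysis of 150 companies

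*Protocol*

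**What the plan says.** Section 7.1 of the protocol states that 150 companies, 100 intervention and 50 control, "will provide 90% power at a 5% level of significance to detect a minimum 0.48-unit difference between two randomised groups". The Overview gives the same figure and adds the cluster size: "with a minimum of 10 products per company, will provide 90% power at a 5% level of significance". Both places then turn to uptake: "We estimate that about half of the intervention companies will participate in the intervention programme, which will reduce the effective sample size". The next sentence draws the consequence: "A total of 100 companies (50 intervention and 50 control companies) will provide 80% power to detect the expected effect size", on the primary outcome and under unchanged assumptions.

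Section 7.2 fixes the analysis set: "All 150 randomised companies will be included in the primary ITT analysis". Section 7.2.2 keeps every company in its allocated group. A comparison restricted to participating intervention companies also appears in section 7.2, as the per-protocol analysis. Participation there means agreeing to take part and attending at least one meeting.

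**The concern.** Non-participation does not shrink an ITT sample. The HSR data come from Nutritrack and FoodSwitch and do not depend on company consent (section 7.4.3), so an intervention company that declines the programme still supplies an outcome and is still counted in the intervention arm. What shrinks is the expected difference between the arms. The sample size text does the opposite: it removes 50 companies and leaves the effect at 0.48.

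Two things are at stake. A null ITT result would be read against a claimed power of 80 to 90%, which may not apply to that analysis. And the Overview makes the cost-effectiveness evaluation conditional on success on the primary outcome, with only a costing analysis otherwise, so the real power of the ITT test also governs whether that work is done.

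**Working it through.** **Inputs.**
- Effect, section 7.1: "detect a minimum 0.48-unit difference between two randomised groups in the mean HSR of all packaged food and beverage products".
- Variability, section 7.1: "a standard deviation (SD) of 1.25, and an intra-cluster correlation (ICC) between products produced by the same company of 0.4".
- Cluster size: 10 products per company, the minimum given in the Overview.
- Test, section 7.2.2: "Statistical tests will be two-sided at a 5% significance level".
- Allocation 100:50; expected uptake about 50%.

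**Formulae.** Variance of a company mean = SD² × (1 + (m − 1) × ICC)/m. SE of the difference = √(variance × (1/n₁ + 1/n₂)). Power ≈ Φ(difference/SE − 1.96).

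**Company-mean variance.** 1.25² × (1 + 9 × 0.4)/10 = 0.71875, an SD of 0.848.

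**Reproducing the protocol's figures.**
- 100 v 50 at 0.48: SE = √(0.71875 × 0.03) = 0.1468; 0.48/0.1468 = 3.27; power 90.5% (90.1% with a t distribution). This matches the stated 90%.
- 50 v 50 at 0.48: SE = √(0.71875 × 0.04) = 0.1696; 0.48/0.1696 = 2.83; power 80.8% (t: 80.0%). This matches the stated 80%.

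Both calculations are correct as sums. The 80% arises only if the 50 non-participating companies are deleted and the full 0.48 is kept, which is the per-protocol comparison.

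**Primary ITT analysis, reading A: 0.48 is the ITT difference.** Unadjusted power is the 90% above and uptake calls for no reduction. At 50% uptake with no effect in non-participants, participants must gain 0.48/0.5 = 0.96 stars, which is 0.96/2.95 = 33% of the assumed mean. The protocol describes an increase of about 16%.

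**Primary ITT analysis, reading B: 0.48 is the effect in participants, and non-participants have none.** The ITT difference is 0.5 × 0.48 = 0.24; 0.24/0.1468 = 1.63; unadjusted power 37% (t: 37%). Varying the inputs:
- Uptake of 40%, 60%, 70% or 80%: 26%, 50%, 63% or 74%.
- Products per company of 20 or 50, or without limit, at 50% uptake: 39%, 41% or 42%.
- For 80% unadjusted power with 150 companies at 50% uptake, participants would need to gain about 0.82 stars.

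**Reading B with baseline adjustment.** Section 7.2.2 includes the baseline outcome value in the model; the sample size calculation does not use it. As an approximation, multiply the company-mean variance by (1 − r²), where r is the company-level correlation between baseline and follow-up. The documents give no r, so these values are assumptions:
- r = 0.5: SE 0.1272; power 47%.
- r = 0.7: SE 0.1049; power 63%.
- r = 0.8: SE 0.0881; power 78%.
- r = 0.9: SE 0.0640; power 96%.

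Power reaches 50% where SE = 0.24/1.96 = 0.1224. That gives 1 − r² = 0.695, so r is about 0.55.

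**The case against.** The strongest reply is that section 7.1 words 0.48 as a difference between randomised groups. Taken literally this is the ITT contrast, and the 90% is then correct for the primary analysis. That stands as a possible reading. It does not rescue the second paragraph, because under it there is no smaller sample to allow for and 80% is still not the ITT power. Nor does it fit the reuse of 0.48, under the same assumptions, for the 50 participating companies. With 50% uptake and no effect in non-participants, 0.48 cannot be both the average over all 100 intervention companies and the average over the 50 that take part.

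A reader might infer that the trial simply has 37% power and would miss a true 0.48-star effect in participants most of the time. The documents do not support that as a settled result, for three reasons. It needs reading B, which the protocol implies but does not state. It needs zero effect in non-participants, which the protocol nowhere asserts; if they gained half the participants' effect, the ITT difference would be 0.36 and unadjusted power 69%. And it ignores the planned baseline adjustment: with it, missing the effect more often than not requires r below about 0.55.

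It is also fair to say that the protocol discloses the expected uptake, labels the second figure openly as 50 v 50, and plans a matching per-protocol analysis. Section 7.2.2 requires 95% confidence intervals, which would show how imprecise a null result was. None of this makes 80% the power of the primary analysis.

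**Conclusion.** Wrong as written. On neither reading of 0.48 is 80% the power of the primary ITT analysis; it is the unadjusted power of the 50 v 50 per-protocol comparison. This conclusion rests only on the protocol's own inputs and its definition of the analysis sets.

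The size of the gap is conditional. Unadjusted ITT power is 90% if 0.48 is the ITT difference, at the price of an implied gain of about 0.96 stars in participants. It is about 37% if 0.48 is the participants' effect and non-participants show none. In that second case the planned baseline adjustment could leave power still under 50% or lift it above 90%, depending on a correlation that the protocol does not give. The analysis set, the model and the estimates are unaffected; what fails is the stated power.

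**What to change.** In section 7.1 and in the study power text of the Overview:
- Relabel the 80% as the power of the 50 v 50 per-protocol comparison.
- State whether 0.48 is the ITT difference or the effect in participating companies. If it is the ITT difference, add that it corresponds to about 0.96 stars in participants at 50% uptake with no effect in non-participants.
- State ITT power for the diluted effect over a range of uptake, both unadjusted and baseline-adjusted. Preferably estimate the correlation from earlier Nutritrack and FoodSwitch waves, before outcome data are merged with allocation; otherwise show a range.

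The cost is a wording change and a short recalculation. No extra companies are needed and the analysis does not change. The stated power for the diluted effect becomes less favourable unless the correlation proves high.
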